6.5 PARTICIPANT COMPLIANCE

At each visit participants will bring back the used and unused study drug and will be asked about compliance. Participants will be asked to detail drug compliance over the past 30 days using a diary card to record the number of capsules taken and to indicate any reason for non-compliance. Compliance will be assessed according to the diary card however a pill count will also take place. This information will be collected on the CRF.

Non-compliance to the protocol study procedures will be documented by the investigator and reported to the sponsor as required in section 14.2. Persistent non-compliance may lead the participant to be withdrawn from the study. Follow up as per the protocol will be attempted for all non-compliant participants.

Primary analyses will be intention-to-treat (ITT) using a dataset of all randomized participants, irrespective of treatment actually taken. A complete case approach will be taken for missing data in analysis of each outcome. Participants will be considered compliant with treatment if they reported taking, on average, at least 90% of their prescribed medication in the 30 days preceding each visit.

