Visit Number 5: Week 24 (+/- 2 weeks) Trial participants return to the research clinic and the following assessments will be completed: safety bloods (Cr&E,FBC,Hb, LFT inc. ^YGT) compliance assessment relapse assessment (count/grade) adverse events concomitant medication

Trial participants will receive their next prescription.

Anticipated visit duration = 20 minutes

Core Brain MRI and CSF neurofilament and CSF lymphocyte phenotyping **sub study** All patients will undergo the 24 week (6 month) brain core MRI scan +/- 14 days of visit 5. WOCBP will have a urine pregnancy test prior to their MRI, compliant with National Guidelines for MRI.

Those patients consented to the CSF neurofilament and CSF lymphocyte phenotyping sub study will have their blood and urine sampled +/- 14 days of visit 5.

Visit Number 6:

Week 36 (+/- 2 weeks)

Trial participants return to the research clinic and the following assessments will be completed:

safety bloods (Cr&E,FBC,Hb, LFT inc. [¥]GT, serum biomarkers [UCL]) compliance assessment relapse assessment (count/grade) adverse events concomitant medication

Trial participants will receive their next prescription.

Anticipated visit duration = 20 minutes

Visit Number 7:

Week 48 (+/- 2 weeks)

Trial participants return to the research clinic and the following assessments will be completed:

safety bloods (Cr&E,FBC,Hb, LFT inc. [¥]GT,serum biomarkers [UCL]) compliance assessment relapse assessment (count/grade) adverse events concomitant medication physical examination vital signs

They will undertake the following assessments *EDSS [assessing physician] MS Functional Composite (MSFC - 9HPT,25TFW,PASAT) Symbol Digit Modalities Test (SDMT) Sloan Low contrast visual acuity (SLCVA) Multiple Sclerosis Impact Scale v2 (MSIS29) Multiple Sclerosis Walking Scale v2 (MSWS) NFI

> Sponsor No.12/0219 v7 Page **50** of **73**

NPRS, BPI and NPS Health economic questionnaire (EQ-5D)

*A telephone EDSS assessment (assessing physician or nurse) is permissible if the participant is unable to attend clinic, however the participant should attend their appointments wherever possible and the EDSS be conducted face-to-face.

Trial participants will receive their next prescription.

Anticipated visit duration = 60 minutes.

CSF Neurofilament and CSF lymphocyte phenotyping **Sub-study** Patients consented to the CSF neurofilament and CSF lymphocyte phenotyping sub study will have their **CSF**, blood and urine sampled +/- 14 days of visit 7.

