9.1 SAMPLE SIZE CALCULATION

9.1.1 Primary MRI Outcome, PBVC

A total of 440 patients will be randomised equally (1:1:1:1) between the three active treatments and the placebo to give 110 per treatment arm. The primary analysis will be intention-to-treat (ITT) on the whole study cohort (n=110/arm). Based on two UK phase II trials (Lamotrigine ⁶⁰ and MS-STAT ²⁷), we expect 10% of the total cohort to drop out of the trial before Year 2, and a further 10% of the total cohort to come for their Year 2 visit, but be off medication. Thus we anticipate 90 patients per arm completing the study.

From the calculations reported in by Altmann et al ⁴³ for measurement of PBVC using the SIENA registration-based method, and further data provided by [name] summarised in the table below (Table A), 90 patients per arm would give over 90% power to detect a 40% reduction in PBVC on any active arm compared to placebo and 80% power to detect a 35% reduction (Bonferroni adjustment for multiple comparisons of three 1.67% two-sided tests, giving 5% overall two-sided significance level). While these sample sizes are based on annual measurement time points and comparison of mean rates of change using longitudinal linear mixed models, Altmann et al also confirm that they are almost identical to the sample size requirements under analysis of covariance of PBVC adjusting for baseline value, the proposed method of analysis in this trial.⁴³

MRI measurement tir	Baseline, 96 weeks						
2-sided significance	0.0167		0.05				
Statistical power		80%	90%	80%	90%		
Treatment effect	30%	123	158	92	123		
	35%	90	116	68	91		
	40%	69	89	52	70		

Table A - Required sample size per arm by treatment effect size, significance level and statistical power; treatment effect expressed as relative mean difference in PBVC under treatment. PBVC assessed using SIENA registration-based method.

For a more exploratory analysis without adjusting for multiple comparisons, this sample size will give almost 90% power to detect a 35% reduction in atrophy. The study is not powered to detect differences between the three active treatment arms.

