9.2.2 Primary MRI Outcome Measure

The primary endpoint will be the percentage brain volume change (PBVC) measured using the Structural Image Evaluation, using Normalization, of Atrophy (SIENA) method between baseline and 96 weeks. A normal linear model will be used to compare the three active treatment group arms with placebo adjusting for baseline normalised brain volume and minimisation variables: age, gender, treatment centre (as a fixed effect) and baseline EDSS. The efficacy measure for each active treatment will be the mean difference in PBVC change versus placebo. All patients for whom baseline and 96 week brain volume data are available will be included in the analysis according to the treatment group to which they were randomised irrespective of which treatment(s) they may have received. Dunnett's method will be used to adjust for the multiple pairwise comparisons versus a common placebo group. No formal comparison of the active treatments will be undertaken.

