9.2.3 Secondary MRI Outcome

9.2.3.1 Pseudoatrophy:

Using the same methods as for the primary MRI outcome, the mean difference in PBVC from baseline to 6 months between the placebo group and each of the active treatment groups will also be assessed. If the reduction in PBVC is significantly greater in any treatment group a secondary analysis will compare PBVC from week 24 to week 96 between that treatment group and the placebo group using normal linear modelling as in section 9.2.2. As this is an exploratory secondary analysis, no formal adjustment for multiplicity will be made.

9.2.3.2 Counts of new and enlarging T2 lesions:

Each active treatment group will be compared with placebo in terms of the number of new and enlarging T2 lesions between the baseline and 96 week MRI. Over-dispersed Poisson regression models will be used to estimate the percentage difference in new/enlarging lesion count after adjusting for baseline T2 lesion volume and the minimisation variables: age, gender, treatment centre and baseline EDSS.

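### The primary PBVC analysis is labelled ITT on 110 per arm but fixed as complete case on about 99; using the week-24 scan of later drop-outs would be a cheap improvement

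*Protocol*

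**What the plan says.** The protocol describes the primary analysis set in three places.

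- Section 6.5: "Primary analyses will be intention-to-treat (ITT) using a dataset of all randomized participants, irrespective of treatment actually taken". The next sentence reads "A complete case approach will be taken for missing data in analysis of each outcome".
- Section 9.1.1: "The primary analysis will be intention-to-treat (ITT) on the whole study cohort (n=110/arm"). The same paragraph expects 10% of the cohort to drop out before Year 2 and a further 10% to attend Year 2 off medication, and bases power on 90 per arm.
- Section 9.2.2: "All patients for whom baseline and 96 week brain volume data are available will be included in the analysis", by randomised arm. The model has one response, the change from baseline to week 96, "adjusting for baseline normalised brain volume and minimisation variables: age, gender, treatment centre (as a fixed effect) and baseline EDSS". It has no week-24 term.

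On the week-24 scan, section 7.2 (Visit 5) says "All patients will undergo the 24 week (6 month) brain core MRI scan". Section 9.2.3.1 uses it to compare "the mean difference in PBVC from baseline to 6 months between the placebo group and each of the active treatment groups", as a check for pseudoatrophy. The week-24 to week-96 comparison in that section is conditional and also needs a week-96 scan.

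**The concern.** The label and the set analysed differ. A reader of 6.5 or 9.1.1 is told that all randomised patients enter the primary analysis. Under 9.2.2, anyone without a 96-week scan is left out.

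This matters beyond wording. A patient who leaves after week 24 has an atrophy value measured by the same technique as the primary outcome, and the primary model ignores it. Complete case then relies on drop-out being unrelated to outcome given the baseline covariates, or at least on any dependence cancelling between the arms. If patients with faster early atrophy leave an active arm more readily than they leave placebo, the remaining active patients look better than the arm as randomised, and the drug effect is overstated. If the selection is in the placebo arm, the effect is understated. A model that includes week-24 PBVC rests on a weaker assumption and needs no new data.

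**Working it through.** **1. Number analysed.** 110 × 0.90 = 99 per arm with a week-96 scan. Removing the further 10% off medication gives 110 × 0.80 = 88, which the protocol gives as about 90.

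**2. Table A of section 9.1.1.** The protocol states no SD, so the ratio of SD to mean PBVC was solved from each cell:

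SD/mean = effect × √(n/2) / (z for alpha + z for power).

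For a 35% effect, alpha 0.0167, 80% power and n = 90: 0.35 × √45 / (2.393 + 0.842) = 0.726. The 12 cells give 0.725 to 0.730, mean 0.727. Working back, n = 2 × (0.727/0.35)² × 3.235² = 90.3, so 91 (stated 90). A 40% effect at 90% power gives 89.2, so 90 (stated 89). The table is internally consistent.

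**3. Power.** Power = Φ(effect/0.727 × √(n/2) − 2.394), with alpha 0.05/3.

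| n per arm | 35% effect | 40% effect |
|---|---|---|
| 90 | 79.8% | 90.3% |
| 99 | 84.0% | 93.0% |
| 110 | 88.0% | 95.4% |

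The stated power uses 90, so it does not depend on analysing 110.

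**4. Bias of complete case.** Assumptions that are not in the documents:

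- the correlation r between week-24 and week-96 PBVC is 0.3 to 0.7;
- in one arm the log-odds of drop-out rise by b = 0.5 to 1 per SD of worse week-24 PBVC;
- drop-out in the other arm is random.

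Let δ be the mean week-24 value, in SD units, among those who stay. With Z standard normal and p(Z) = 1/(1 + exp(−(c − bZ))), where c is set so that the mean of p is the drop-out rate d, δ = E[Z(1 − p(Z))]/(1 − d). The bias, as a fraction of the placebo mean change, is r × 0.727 × δ. Dividing by 0.35 gives the share of a 35% effect.

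| d | b | δ | share at r = 0.3 | share at r = 0.7 |
|---|---|---|---|---|
| 10% | 0.5 | 0.0488 | 3.0% | 7.1% |
| 10% | 1 | 0.0908 | 5.7% | 13.2% |
| 20% | 0.5 | 0.0962 | 6.0% | 14.0% |
| 20% | 1 | 0.1732 | 10.8% | 25.2% |

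For example, 0.7 × 0.727 × 0.0908 = 0.0462, and 0.0462/0.35 = 13.2%. The standard error of the contrast is 0.727 × √(2/99) = 0.103, so at 10% drop-out the bias is 0.10 to 0.45 standard errors.

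Two comparisons frame this. If b and d are the same in both arms, the shifts cancel and the bias is about 0. If b is the same but drop-out is 20% on active and 10% on placebo, the difference in δ is 0.0474 (b = 0.5) to 0.0824 (b = 1). The bias is then 3% (r = 0.3, b = 0.5) to 12% (r = 0.7, b = 1) of the effect.

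**5. What a model with week-24 PBVC recovers.** In large-sample simulation (2 million per arm, 10% drop-out):

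- If drop-out depends on week-24 PBVC and every drop-out has that scan, the bias is about 0.
- If half of the drop-outs leave before week 24, about half of the complete-case bias remains.
- If drop-out depends on the unseen week-96 value and differs by arm, complete case is off by 0.05 to 0.10 of the placebo mean change and the two-visit model by 0.02 to 0.09.

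**6. Precision.** Effective n = 110 / [(1 − r²)/0.9 + r²], which gives 99.9, 101.5 and 104.1 for r = 0.3, 0.5 and 0.7, against 99 for complete case. The gain is about 1 to 5 patients per arm.

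**The case against.** The case for leaving the plan alone has several parts.

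- **It is mainly a label.** Section 6.5 states complete case straight after ITT, and 9.2.2 says exactly who is analysed, by randomised arm. This stands in part: a careful reader can work out the set. But n = 110 per arm is still not what would be analysed.
- **Missing data are limited and will be examined.** Section 5.5.3 keeps patients who stop drug in follow-up with a week-96 scan, and 9.2.1 compares missingness by arm. This reduces the problem but offers no remedy if the arms differ. The schedule in 7.2 also says that the end-of-study MRI must take place on study drug, which does not fit 5.5.3 or 9.1.1. Those sections must be reconciled, since the schedule wording could tie missing scans to stopping treatment.
- **Section 9.2.6 leaves missing-data methods to the SAP.** The SAP is not at hand and may add sensitivity analyses. But 6.5 and 9.2.2 already fix the primary method.
- **Differential selection is speculative.** The trial is double blind and no section makes continuation depend on PBVC. This stands, and it is why the point is a risk and not a demonstrated bias.
- **It is late.** Version 7 is dated June 2018, recruitment is complete and the trial is due to end in October 2018. This bears on timing: the change must be documented before unblinding.

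Stronger readings are tempting. A reader might infer that any link between drop-out and atrophy biases complete case; equal selection at equal rates leaves the contrast about unbiased. A reader might infer that the week-24 data would remove the bias entirely; section 6.4 places titration and most re-challenge before week 24, so early leavers without that scan are plausible. A reader might also infer that the trial loses its planned power; it was powered on 90 per arm.

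**Conclusion.** The point holds as a cheap improvement. The protocol names one analysis set and fixes another, about 99 per arm instead of 110, and its primary model sets aside an outcome measurement already planned for everyone.

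At the planned 10% drop-out, the possible bias is about 3% to 13% of a 35% effect, in either direction, when selection acts in one arm only. It is about zero when selection and drop-out rates are equal across arms, and up to about 25% if active-arm drop-out reaches 20% with strong selection. The correlation and the selection strength are assumptions. Nothing in the documents shows that drop-out will follow early atrophy, or that it will differ by arm. The stated power is unaffected.

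**What to change.** In 6.5 and 9.2.2, replace complete case for PBVC with a repeated-measures linear model of the changes from baseline to week 24 and from baseline to week 96. Include arm by visit, an unstructured covariance and the covariates of 9.2.2, and take the Dunnett-adjusted week-96 contrast as primary. Keep the present complete-case model as a sensitivity analysis, and add one for missingness that depends on unseen week-96 values. In 6.5 and 9.1.1, describe the set actually analysed: all randomised patients with at least one post-baseline scan, by randomised arm. That set is still not everyone randomised, and the text should say so.

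The cost is protocol and SAP wording, settled before unblinding, and slightly more complex code. The model assumes data missing at random given week 24, which is weaker than the present assumption but still an assumption. The correction is only partial for patients who leave before week 24 or whose drop-out depends on unseen values, and the gain in precision is small.

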6.6 OTHER MEDICATIONS

6.6.1 Non-Investigational Medicinal Products

Participants in the CSF and lymphocyte phenotyping sub study will be administered a local anaesthetic prior to lumbar puncture. The anaesthetic is classed as a NIMP. This trial will not be using any Non Investigational Medicinal Products (NIMPs) other than in the CSF and lymphocyte phenotyping sub study.

6.6.2 **Permitted Medications**

All medications are permitted, apart from those outlined in section 6.3. Where required, for example to treat a relapse, patients on trial treatment and in follow up can receive steroid therapy.

The following should be used with caution as drug interactions are possible:

- Angiotensin-converting inhibitors
- NSAIDs
- Ciclosporin
- Inhibitors of CYP 1A2 (e.g. caffeine, diclofenac, diazepam, nicergoline, clomipramine, imipramine, fluvoxamine, phenacetin, theophylline, amitriptyline and quinolones)
- Inducers of CYP 1A2 (e.g. cigarette smoke, charcoal-broiled food, rifampicin and omeprazole) could increase the rate of riluzole elimination

6.6.3 **Prohibited Medications**

Since the patients will be blinded to the IMP, all individual absolute contraindicated drugs are absolutely contraindicated as a whole. All 'use with caution' are 'use with caution' as a whole.

Amiloride

Absolute contraindications:

MS-SMART Version 7 4th June 2018

- Lithium
- Chlorpropamide
- Potassium supplements
- Potassium retaining diuretics e.g. triamterene, spironolactone

Riluzole

No absolute contra-indications

Fluoxetine

Absolute contra-indications:

- Monoamine oxidase inhibitors
- Phenytoin
- L-tryptophan) and/or neuroleptic drugs
- Lithium
- SSRI anti-depressants
- Metoprolol

Use with caution:

CYP2D6 isoenzyme inhibitors: (such as flecainide, encainide, carbamazepine and tricyclic antidepressants), should be initiated at or adjusted to the low end of their dose range.

Tamoxifen efficacy maybe reduced

Drugs that prolong the QT interval should be used with caution.

Care with Oral anticoagulants, CYPROHEPTADINE, DRUGS INDUCING HYPONATREMIA AND DRUGS LOWERING THE EPILEPTOGENIC THRESHOLD.

St John's Wort:

If treatment of in-trial depression is needed, the following are allowable (that is can be safely added to fluoxetine): mirtazapine. venlafaxine, duloxetine and agomelatine.

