On rare occasions, development of a serotonin syndrome or neuroleptic malignant syndrome-like events have been reported in association with treatment of fluoxetine, particularly when given in combination with other serotonergic (among others, L-tryptophan) and/or neuroleptic drugs. As these syndromes may result in potentially life-threatening conditions, treatment with fluoxetine should be discontinued if such events (characterised by clusters of symptoms, such as hyperthermia, rigidity, myoclonus, autonomic instability with possible rapid fluctuations of vital signs, mental status changes, including confusion, irritability, extreme agitation, progressing to delirium and coma) occur and supportive symptomatic treatment should be initiated. The risk of this is very low and was not reported in the two phase IIa clinical studies of fluoxetine in multiple sclerosis.^{18, 20}

Drug withdrawal: The SPC reports that withdrawal symptoms when treatment is discontinued are common, particularly if discontinuation is abrupt. In previous phase IIa clinical studies of fluoxetine in multiple sclerosis ¹⁸ ²⁰ they did not report any withdrawal reactions upon discontinuation of long term use of Fluoxetine. Based on these previous studies^{18, 20}, gradual dose reduction in this protocol will not occur on the last treatment visit, however, participants will be followed by telephone 1 month after terminating the study to ascertain any issues with terminating the medication Participants are also reminded in the Participant Information Leaflet (PIL) to contact the study team if there are any withdrawal symptoms.

Risk minimisation: standard monitoring and treatment of nausea, diarrhoea and headache will be provided as needed. Patients with renal failure or hepatic failure are excluded from the trial. If clinically significant LFT changes occur during the trial, or creatinine>130mmol/l, the steps outlined in section 6.7.3 (Management of Laboratory Abnormalities) will be followed. FBC monitoring (including neutrophil count) is part of the safety blood panel, and the steps outlined in section 6.7.3 will take place if the neutrophil level falls below <1.0 x10⁹ /l or the platelet level reduces to <50 x10⁹ /l.

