1.2.2.3. Amiloride

Is a widely used diuretic and acid sensing ion channel (ASIC) blocker, with recently recognised myelo and neuroprotective effects in both human and experimental models of progressive MS.

Clinical Trial: Phase IIa: 17 patients with Primary Progressive MS (PPMS) participated in a pretreatment (1 yr) and amiloride treatment phase (1 yr) at 5mg bd.^{24,25} In the amiloride-treatment year, there was a significant reduction in the whole brain atrophy rate compared to pre-treatment (p=0.009). Corpus callosal radial diffusivity (myelin integrity) and thalamic mean diffusivity (structural integrity) were also significantly improved.

Dosing and Safety: It has been used as a potassium sparing diuretic since it was first introduced in 1967 and has an extremely good side-effect profile, with the main contraindications related to occasional hyperkalaemia e.g. avoidance of drugs such as triamterene, spironolactone, and usage in renal failure.²⁶

Dose justification: the dose used in the trial above was 5mg bd. This dose will therefore be used for this trial.

Side-effects: Amiloride is usually well tolerated, although minor side-effects are reported relatively frequently. Apart from hyperkalaemia, significant adverse reactions have been infrequently reported. Nausea/anorexia, abdominal pain, flatulence and mild skin rash are probably due to amiloride; but other side-effects are generally associated with diuresis or with the underlying disease being treated.

Risk minimisation: patients with renal failure or hepatic failure are excluded from the trial. If the plasma potassium exceeds 5.5mmol/l or plasma sodium <125mmol/l or creatinine>130mmol/l, patients will not be able to enter the trial. If these parameters are breached during the trial, the steps outlined in section 6.7.3 will be followed. Potassium conserving drugs and potassium supplements are prohibited (see above). Vital signs will be observed to ensure significant hypotension or hypovolaemia does not occur during the trial. Patients will be advised to avoid dehydration and the volume status will be carefully monitored of the patients. Other symptoms will be monitored as per routine best medical practice.

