6.3 DOSING REGIME

Following randomisation, study drug will be dispensed by the site pharmacy.

Patients are prescribed 1 capsule a day (OD), orally at baseline. At 1 month they will up-titrate to 1 capsule twice a day (bd) orally for the remainder of the study; no relationship to food is required.

That is:

- Fluoxetine 20 mg twice per day (20 mg once per day for first 4 weeks)
- Riluzole 50 mg twice per day (50 mg once per day for first 4 weeks)
- Amiloride 5 mg twice per day (5 mg once per day for first 4 weeks)
- Placebo –1 capsule twice per day (1 capsule once per day for first 4 weeks)

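### Sections 6.6.2 and 6.6.3: a wrong pointer to the banned drugs, one SSRI left on a caution list, and an unqualified *safely* for antidepressants added to fluoxetine

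*Protocol*

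**What the plan says.** Four places in the Protocol bear on what a site may prescribe alongside blinded study drug.

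- **Section 6.6.2, Permitted Medications**, gives the general rule: "All medications are permitted, apart from those outlined in section 6.3". It then lists drugs to use with caution. Among the CYP 1A2 inhibitors are "clomipramine, imipramine, fluvoxamine, phenacetin, theophylline, amitriptyline and quinolones".
- **Section 6.3, Dosing Regime**, is the place that rule points to. It covers the capsule schedule, for example "Patients are prescribed 1 capsule a day (OD), orally at baseline", and names no concomitant drug.
- **Section 6.6.3, Prohibited Medications**, holds the actual bans. It opens with "Since the patients will be blinded to the IMP, all individual absolute contraindicated drugs are absolutely contraindicated as a whole". Its absolute contraindications for fluoxetine include "SSRI anti-depressants". It closes with the rule for depression arising during the trial: "If treatment of in-trial depression is needed, the following are allowable (that is can be safely added to fluoxetine): mirtazapine. venlafaxine, duloxetine and agomelatine".
- **Section 1.2.2.1, Fluoxetine**, warns that serotonin syndrome or similar events have been reported rarely, "particularly when given in combination with other serotonergic (among others, L-tryptophan) and/or neuroleptic drugs". It describes them as potentially life-threatening, tells sites to stop fluoxetine if they occur, and calls the risk very low.

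**The concern.** These are working instructions, not background. One participant in four is on fluoxetine and nobody at the site knows which one, so sites must prescribe as if everyone were. Three things in the text do not fit that need.

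1. The permission rule sends the reader to a section with no bans in it.
2. One named SSRI appears as a caution drug, although the class is banned in every arm.
3. Two serotonergic antidepressants are called safe to add to fluoxetine, although the background section warns about serotonergic combinations.

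At stake is a prescribing decision for a participant who becomes depressed during the trial. A site working from 6.6.2 alone could take fluvoxamine to be allowed. A site working from 6.6.3 alone is not directed to the serotonin-syndrome warning.

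**Working it through.** The protocol gives no figure on this point to reproduce. The check sets the texts side by side, followed by simple arithmetic on scale.

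**Step 1: the pointer.** Section 6.6.2 excepts the drugs in 6.3. Section 6.3 lists doses for the three active drugs and placebo, and nothing else. The bans stand in 6.6.3, so the number is wrong. The likely cause is renumbering. Section 1.2.2.3, on breached laboratory limits, shows the same kind of slip: "If these parameters are breached during the trial, the steps outlined in section 6.7.3 will be followed". Those rules are in 6.6.4. Sections 1.2.2.1 and 1.2.2.2 carry the same outdated number. These laboratory references are clerical only.

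**Step 2: fluvoxamine.** Section 6.6.2 says caution; 6.6.3 bans SSRIs and extends each arm's bans to all arms. By drug class, fluvoxamine is an SSRI. The protocol does not say so, but this is not in dispute. The drug therefore has two statuses. Its entry may have come from riluzole's interactions, since the adjacent item on CYP 1A2 inducers refers to riluzole elimination; that is an inference. The tricyclics on the same list raise no conflict, because 6.6.3 also places tricyclics under caution.

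**Step 3: the word *safely*.** Venlafaxine and duloxetine are serotonin-noradrenaline reuptake inhibitors, again by undisputed drug class. The warning in 1.2.2.1 covers fluoxetine combined with other serotonergic drugs. The protocol acts on that mechanism elsewhere: 6.6.3 bans L-tryptophan, and 1.2.2.1 contraindicates St John's Wort because of serotonergic effects. The permission in 6.6.3 has no cross-reference to the warning and no monitoring instruction. Section 1.2.2.1 notes that no such event was reported in two earlier fluoxetine studies in MS, but the protocol does not say whether anyone in them also took one of these antidepressants.

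**Step 4: checks already in place.**
- Concomitant medication is reviewed at every clinic visit (Schedule of Events, 7.2), and participants are asked at each visit about new medicines (10.2).
- Participants may contact the investigator at any time about symptoms (10.4.6.1), carry a trial card with emergency numbers (5.5.1), and can have unscheduled visits (7.2).
- Fluoxetine is stopped if the syndrome occurs (1.2.2.1).

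The visit checks would pick up a new antidepressant, but only at the next visit. After week 48 the clinic visits are at weeks 72 and 96, so the gaps are 72 − 48 = 24 and 96 − 72 = 24 weeks. The other safeguards depend on symptoms or on the site's judgement.

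**Step 5: scale.**
- Fluoxetine arm: 440 / 4 = 110 (9.1.1 also gives 110 per arm).
- Version 7 is dated 4 June 2018 and the synopsis gives 31.10.2018 as the trial end: 26 + 31 + 31 + 30 + 31 = 149 days, and 149 / 7 = 21.3 weeks.
- Assuming the last week-100 call falls within that end date, the last dose comes 28 days earlier: 149 − 28 = 121 days, and 121 / 7 = 17.3 weeks.
- Anyone still on treatment at version 7 would then be at about week 96 − 17.3 = 78.7 or later, ignoring visit windows.
- Recruitment is complete (1.2.2.1), and entry excluded significant signs of depression and a Beck score of 19 or higher (4.3).
- The documents give no rate of antidepressant use during the trial, so the number affected cannot be calculated.

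**The case against.** The strongest reply is that little here could mislead a site that reads the whole of section 6.6. The heading straight after 6.6.2 is Prohibited Medications, it bans SSRIs in plain words, and it binds all arms. A reader sent to 6.3 would find capsule counts and see that the number is wrong. Fluvoxamine is one example in a list that also contains caffeine; 6.6.2 says nothing about SSRIs as a class. On the antidepressants, 1.2.2.1 does not name venlafaxine or duloxetine, rates the risk very low, and sets a stopping rule rather than a ban. The layout of 6.6.3 is also broken in the extracted text: the permission follows a caution label and an empty St John's Wort entry, so a caution may have been meant to cover it.

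Most of this stands, and it limits the point. It does not remove it. The pointer is wrong, fluvoxamine is listed under the wrong status, and the permission sentence itself says *safely*, wherever the caution label was meant to reach.

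A reader might go further in three ways that the documents do not support:

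- *That nothing is prohibited, or that SSRIs are permitted.* Section 6.6.3 states the bans explicitly, and a class-wide ban would normally override one example on another list.
- *That the four antidepressants should be withdrawn from the permitted list.* Section 1.2.2.1 is a warning, not a ban, and the documents cannot settle how hazardous either serotonergic drug is when added to fluoxetine.
- *That new antidepressant use goes unmonitored.* It is asked about and recorded at every clinic visit.

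**Conclusion.** The point holds as a minor participant-safety correction to the prescribing instructions. The wrong pointer follows from the document alone. The fluvoxamine conflict and the mismatch over *safely* also need undisputed drug-class membership that the protocol does not state.

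The size is small. No more than 110 participants are allocated fluoxetine, and the number who would start an added antidepressant is not estimable. If follow-up ends by the stated date, at most about 17 weeks of dosing remained when version 7 was dated. The primary endpoint, power and analysis are not affected.

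**What to change.** - **6.6.2:** change the reference from section 6.3 to section 6.6.3. Delete fluvoxamine from the caution list, or mark it as prohibited.
- **6.6.3:** keep the four antidepressants, but replace the statement that they are safe to add with wording such as: may be used with caution, treating every participant as if on fluoxetine, with monitoring for serotonin syndrome (see 1.2.2.1).
- **Sites:** send a short note to those with participants still on treatment.
- **Same edit, optional:** correct the section 6.7.3 references to 6.6.4.

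The cost is a few wording changes, one note, and slightly closer follow-up when an antidepressant is started. Eligibility, data collection and analysis do not change.
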